Nurses will receive training including a video as well as comprehensive guidelines. The researcher will visit the care home and provide the training at a time and date convenient to the care home. Community pharmacists and pharmacists who act as a 'back-up' for the study will receive training from the study consultant pharmacist. The research team will remain available for further training and guidance as required throughout the study period.

Using the PADRe Profile with care home residents

Nurse leads in 7 homes will implement the PADRe Profile. They will need to complete the PADRe Profile with each of the residents (up to 26) at least every month, for 3 months as part of normal care. To do this, they will take some observations and ask some questions. All observations and questions are those that are sometimes used as part of normal care and are not invasive. The PADRe Profile checklist will help to determine clinical signs and symptoms of adverse drug reactions. At this time, the nurses will also be asked to complete a record/log/diary of using the PADRe Profile to record how it works during usual care. Both use of the PADRe Profile and recording how it works will take approximately 10 to 25 minutes per resident. We ask nurses that they try to carry out PADRe Profile completion with residents and using existing documentation at least every month or more frequently if medicines are changed. They will then pass it to the prescribers and pharmacists caring for the residents, along with the medication administration records.

Use of the quality of life questionnaire

At the start and end of the study, study nurses will fill in a quality of life questionnaire (the EQ-5D-5L) (Euroqol Group 2009) with the participating residents (EQ-5D-5L English; EQ-5D-5L Welsh https://euroqol.org/eq-5d-instruments/eq-5d-5l-about/). This consists of 5 'tick box' questions and will take approximately 5 minutes. This will determine whether the use of the PADRe Profile has improved (or not) the quality of life of the residents.

Undertaking reviews of the care home residents' nursing and medical notes

Consent for researchers to view patient records will have already been obtained from the residents when they consent to take part in the process evaluation at the start of the study.

The researcher will review these notes using a document review sheet (appendix – review

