notes) before the start of the study and at the end of the study for evidence of use of the new PADRe Profile and any changes in care or outcomes of care.

Introductory and debriefing interviews with care home nurses

Before the implementation of the PADRe Profile, study nurses will be invited to take part in an introductory interview with the researcher who will ask them to discuss their views on medication monitoring and the potential of the PADRe Profile instrument. An interview guide will be used. Their knowledge of medications and adverse drug reactions will not be tested but rather, their views on these as well as their views on the PADRe Profile instrument to be used will be discussed. This interview will take place at the care home and will last approximately 30 minutes. Nurses will also receive a debriefing interview with the researcher at the end of month 2 of the implementation of the PADRe Profile (during its use) and at the end of month 3 of using the PADRe Profile. A separate interview guide will be used for debriefing the study nurses.

Undertaking interviews with the stakeholders

At the end of the study period where the PADRe Profile is used, the researcher will undertake qualitative interviews with stakeholders; 1 GP, 1 Community Pharmacist and 1 Resident Representative from each care home. They will be invited to discuss their experiences of participating in a study where the PADRe Profile is being used. This interview will take approximately 30 minutes and an interview guide will be used.

Study size

We shall introduce medicines' monitoring into 7 care homes, each with 26 residents prescribed >4 medicines (estimated ~90% residents (Jordan et al 2015). In previous work with participants acting as their own controls, de-prescribing occurred in 8.5% more participants (12.1% vs. 3.6%) when ADRe Profiles were used. We hypothesise that the new PADRe Profile will be twice as effective. Based on the reported intra-cluster coefficient (0.02) (Jordan et al 2015), 182 participants will detect this difference with 80% power & 5% significance, allowing for a 5% loss to follow up (Uitenbroek 1997, Killip et al 2004).

Analyses

Both quantitative and qualitative methods of analysis will be used and data will be triangulated.

Statistical analysis

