Differences between before and after the intervention will be calculated for: problems addressed, prescription regimens, NHS use, and compared, adjusting for site (statistician AW). The impact of age, diagnoses, and medicines' use (numbers and types of medicines prescribed8) will be accounted. Resource use, costs, and health economic outcome measures will be described (JR).

Qualitative analysis

Interviews will be analysed by the team using the constant comparative method to identify predictors of successful adoption and any changes to the PADRe Profile, working

arrangements and oversight needed to embed use. This systematic, re-iterative method of comparing and contrasting emerging codes, categories and concepts ensures that theoretical perspectives are embedded in the description of change. Interviews will be coded, categorised, analysed and interpreted by at least two researchers and discussed at team meetings, with guidance and consistency checks.

Diaries/logs will also be analysed in association with interview transcripts.

Ethics

Permission to carry out this study will be given by an NHS Research Ethics Committee.

Following approval, any subsequent amendments will be communicated to the Ethics

Committee as well as the investigators, the study participants, and the trial registry.

Participation in the study is voluntary. All those participating will receive a participant information sheet (PIS) and will need to sign a consent form indicating their understanding of their role in the study. The researcher will also be available to discuss with the participants any questions that they may have.

All participants will be given sufficient time to decide whether they wish to take part. They will be informed that their participation in voluntary and that they are free to withdraw at any time without giving a reason for doing so. Those participants agreeing to be interviewed will be informed that their anonymised data and quotes may be used in any relevant publications.

Care home participants or their representatives will be informed that if they chose to withdraw from the study, their medical care or legal rights will not be affected. They will also be informed that

- sections of their care home health records may be looked at by individuals from Aneurin Bevan University Health Board, Cardiff and Swansea Universities and from regulatory authorities

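### The end-of-study notes review can be prompted by completed PADRe Profiles and diaries while the baseline review cannot, so an uncontrolled before-after comparison may partly measure more complete searching

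*Protocol*

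**What the plan says.** The Protocol section on reviewing residents' nursing and medical notes gives the task to one role: "The researcher will review these notes using a document review sheet". The timing is "before the start of the study and at the end of the study for evidence of use of the new PADRe Profile and any changes". The changes meant are those to residents' care and its results.

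The same role appears elsewhere:
- Training of the nurses: "The researcher will visit the care home and provide the training at a time and date convenient to the care home".
- Debriefing: "Nurses will also receive a debriefing interview with the researcher at the end of month 2", and again at the end of month 3.
- The one interview before implementation asks nurses to "discuss their views on medication monitoring and the potential of the PADRe Profile instrument".
- After the PADRe period, "the researcher will undertake qualitative interviews with stakeholders".

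The review sheet in the appendix is headed as a set of process questions for tracking use of PADRe. It covers completion, storage and omissions of Profiles, then problems marked (Q10), actions marked (Q11), professionals contacted (Q12), care-plan changes (Q13), actions completed (Q14), MAR-chart changes (Q16) and clinical changes (Q17).

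Under Statistical analysis, the comparison is within the treated homes: "Differences between before and after the intervention will be calculated for: problems addressed, prescription regimens, NHS use", adjusted for site. No control group is described.

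**The concern.** Profiles and nurse diaries come into being only once PADRe is in use. At the first review the sheet's Profile questions have nothing to refer to, and the reviewer searches the notes and charts unaided. At the second review the same sheet takes the reviewer through what the Profile flagged before asking which contacts and changes followed. A Profile that marks a problem and an action tells the reviewer what to look for.

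If that makes the second search more complete, more change is recorded after than before even when nothing has altered. A concurrent control would absorb such a shift. Here it stays in the estimate, and adjustment for site, age, diagnoses and medicines cannot remove it. For changes in care the direction favours PADRe. For NHS use the reading is less clear, because extra contacts found could count as action taken or as extra resource use.

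This is separate from the Profile's intended effect of bringing more problems to light in practice. It concerns only how completely the record is searched in each period.

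**Working it through.** **Which sources exist at each review**

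| Source | Baseline review | End review |
|---|---|---|
| MAR charts | yes | yes |
| Nursing and medical notes | yes | yes |
| Completed Profiles | no | yes |
| Nurse logs or diaries | no | yes |
| Month-2 debrief already held | no | yes |

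The sheet asks which Profile items were copied from the notes (Q5), so Profile and notes are read against each other. It allows for Profiles kept in the notes, in a research file or elsewhere (Q2). Work by at least two researchers is stated for the interviews, not for the notes review.

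**The plan's own figure, as context for size.** Study size gives 12.1% vs 3.6% de-prescribing (8.5 points) and supposes twice that effect, read here as 17 points (3.6% vs 20.6%). For two proportions, two-sided 5%, 80% power:

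n = [1.960 × √(2 × 0.121 × 0.879) + 0.842 × √(0.036 × 0.964 + 0.206 × 0.794)]² / 0.17² = 56.6, so 57 per group.

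Design effect = 1 + 25 × 0.02 = 1.5. Total = 57 × 2 × 1.5 = 171, and 171 / 0.95 = 180, close to the stated 182. The 17-point reading is therefore a fair yardstick, and the stated figure is not in dispute.

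**Apparent difference with no true change.** With true rate p in both periods and shares found s₁ (before) and s₂ (after):

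apparent difference = p × (s₂ − s₁).

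The shares are assumptions. The base rate is 3.6%, the only rate given without the Profile, treated here as the true rate.

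- 80% vs 95%: 0.036 × 0.80 = 2.9%; 0.036 × 0.95 = 3.4%; difference 0.036 × 0.15 = 0.54 points. This is 0.54 / 8.5 = 6% of the earlier effect and 0.54 / 17 = 3% of the planned one.
- 70% vs 95%: 0.036 × 0.25 = 0.9 points, that is 0.9 / 8.5 = 11% and 0.9 / 17 = 5%.

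**Free-text items.** The documents give no rates for these. Assumed rates with 80% vs 95% found:

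| Assumed true rate | Reads before | Reads after | Difference | Chance of a significant 'after > before' result |
|---|---|---|---|---|
| 3.6% | 2.9% | 3.4% | 0.5 points | 4% |
| 30% | 24.0% | 28.5% | 4.5 points | 12-16% |
| 50% | 40.0% | 47.5% | 7.5 points | 21-29% |

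With equal completeness the chance in the last column is about 2.5%. The lower figure uses an effective 182 × 0.95 / 1.5 = 115 residents per occasion. The higher is a simulated McNemar test on 173 residents without clustering.

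**Could this alone produce the de-prescribing effect?** Completeness would have to rise 12.1 / 3.6 = 3.4-fold to mimic the earlier difference, and 20.6 / 3.6 = 5.7-fold to mimic the planned one.

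**The case against.** The strongest reply is that the study is an observational process evaluation, the same sheet is used both times, a baseline review is done prospectively and data are triangulated. The order in which a reviewer reads the records then looks like operational detail. The protocol contradicts itself nowhere on this, and no stated figure is wrong. That much stands, and it limits the point to an inexpensive improvement. It does not remove the asymmetry: a common sheet built around Profiles gives prompts only when Profiles exist. Nor is this a matter left to a statistical analysis plan, since the protocol itself fixes the reviewer's role, the timing and the form.

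Three stronger readings are tempting and are not supported.

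- A reader might infer that the researcher arrives at the final review having heard from nurses what changed for each resident. The protocol gives no content for the debriefing guide and does not place the month-3 debrief before the final review. It also never defines the researcher as a single person. That Profiles and diaries act as leads is itself inferred from what exists when, and from the layout of the sheet.
- A reader might start the illustration from 12.1%, giving 12.1 × 0.15 = 1.8 points, or 21% of the earlier effect. But 12.1% was the rate with the Profile in use, so it is the wrong base for a no-effect scenario.
- A reader might conclude that the de-prescribing result is seriously threatened. MAR charts exist in both periods and are the least affected source, and a 3.4-fold to 5.7-fold gain in completeness is unlikely.

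**Conclusion.** The concern holds in a limited form. The search before is unprompted and the search after can be prompted. Without a control group, any resulting difference in completeness passes straight into the before-after contrast. It matters mainly for changes in care, clinical changes and NHS contacts read from free-text notes, although the protocol does not spell out the source for NHS use. For de-prescribing read from MAR charts it is small: about 0.5 points under an assumed 80% vs 95%, and 0.9 points under 70% vs 95%. For commoner free-text items the shift could reach several points, but both the rates and the completeness behind that are assumptions. The documents establish that the asymmetry exists, not how large it is. It is worth correcting because the correction is cheap.

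**What to change.** Split the review sheet into two passes and state the order in the protocol.

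1. At both reviews, over equal and dated look-back windows, first complete the record-based items (Q12, Q13, Q16, Q17 and NHS use) from MAR charts and care notes only.
2. At the end review, do this before consulting Profiles and diaries, wherever these are filed separately from the notes.
3. Then complete the Profile-based items (Q1-Q11 and Q14).
4. Flag any change found only through a Profile or diary, and report it separately from the before-after comparison.

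The cost is slightly more work per resident; no extra assessor is needed. The bias is reduced, not removed. The reviewer still knows which period is being read, and the researcher role has still held the month-2 debrief. Profiles filed in the notes cannot be avoided, and the outcome of problems addressed remains exposed because it rests largely on the Profile-based items. The report should state these limits.

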1. I confirm that I have read and understood the in (version XX) for the above study. I have had the op ask questions and have had these answered satisfa	portunity to consid		
I understand that my participation is voluntary a time without giving any reason.	ind that I am free to	o withdraw at any	
3.I am happy for the interview to be recorded and information used to inform development of medic	•	e researchers, and the	
4. I agree to the use of anonymised data and quothe the use of a study number assigned to my details.	otes in any relevar	nt publications, and to	
5. I agree to take part in the above study.			
Name of participant (PRINT)	Date	Signature	
Name of person taking consent (PRINT) When completed: 1 for participant: 1 for researcher site file	Date	Signature	

Process questions (review notes) to track use of PADRe.

We shall retrieve information for each PADRe Profile item (attached).

Q1.	How often are PADRe Profiles completed? N in weeks
Q2.	Where stored? Notes / research file / other
Q3.	Note items omitted. LIST
Q4.	Other discrepancies y/n LIST
Q5.	Note which items copied from notes, if possible. LIST
Q6.	Guidelines used y/n
Q7.	Any equipment missing for vital signs? y/n
Q8.	If so, which
Q9.	Profiles juxtaposed with MAR charts? y/n
Q10.	Problems marked LIST n
Q11.	ACTIONS marked LIST n
Q12.	Professionals contacted LIST n
Q13.	Care plan changes LIST n
Q14.	Actions completed LIST n
Q15.	Evidence of pharmacist / prescriber review? y/n
Q16.	Changes in MAR charts LIST n
Q17.	Clinical changes LIST n
Q18.	Any other instruments used to record ADRs? y/n NAME
